### **3.5.3 Other Co-Variates/Control Variables**

Baseline demographics and clinical characteristics will be used in statistical analysis models.

### **3.5.4 Derived Variables**

- Number of consultations/visits to healthcare professionals for treatment of RA, categorized by the treatment department
  - ✓ General Practitioner (Taiwan: Family Medicine)
  - ✓ Rheumatologist
  - ✓ Gerontologist

- ✓ Orthopedist
  - ✓ Internist
  - ✓ Emergency department
  - ✓ Traditional Medicine
  - ✓ Physical therapist (Taiwan: Rehabilitation Medicine)
  - ✓ Other
- Number of procedures received when visiting the healthcare professional(s) for treatment of RA
  - ✓ Chest X-Ray
  - ✓ Spine X-Ray
  - ✓ Neck X-Ray
  - ✓ Shoulder X-Ray
  - ✓ Hand X-Ray
  - ✓ Knee X-Ray
  - ✓ MRI
  - ✓ CT scan
  - ✓ Electrocardiogram
  - ✓ Blood sample taken
  - ✓ Urine test
  - ✓ Endoscopy
  - ✓ Bone scan
  - ✓ Liver function test
  - ✓ Tuberculin Skin Test
  - ✓ Sputum tests
  - ✓ Other
- Number of surgeries received when visiting the healthcare professional(s) for treatment of RA
  - ✓ Arthroscopy
  - ✓ Carpal tunnel release
  - ✓ Cervical spinal fusion
  - ✓ Total knee replacement
  - ✓ Total hip replacement
  - ✓ Knee arthrodesis (fusion)
  - ✓ Hip arthrodesis (fusion)
  - ✓ Synovectomy
  - ✓ Other
- Number of hospitalizations in relation to RA

- Length of stay: total days in hospital in relation to RA
- Number of concomitant medications taken for RA
- Disease Modifying Antirheumatic Drug (DMARD)
  - ✓ Auranofin (Ridaura, Myochrysine)
  - ✓ Azathioprine (Imuran)
  - ✓ Cyclosporine (Sandimmune and Neoral)
  - ✓ Hydroxychloroquine (Plaquenil)
  - ✓ Leflunomide (Arava)
  - ✓ Methotrexate (Rheumatrex, Folex)
  - ✓ Minocycline (Minocin, Dynacin and Vectrin)
  - ✓ Sulfasalazine (Azulfidine)
  - ✓ Others

#### Anti-inflammatory Drug (NSAID)

- ✓ Ibuprofen (Advil, Motrin, Nuprin)
- ✓ Naproxen (Naprosyn, Anaprox, Aleve)
- ✓ Celecoxib (Celebrex)
- ✓ Aspirin (ASA)
- ✓ Diclofenac (Voltaren)
- ✓ Indomethacin (Indocid)
- ✓ Others

#### Others

- ✓ Steroids
- ✓ Stomach or gastric medications

### 3.5.5 *Conventions*

Given the real world nature of the data, multiple imputation methods for missing data will introduce bias as missing data cannot be considered completely at random (MCAR) or at random (MAR). Due to the observational nature of this study, non-imputing process will be applied, except with date data where the exact day is missing; day “15” will be assumed. Efficacy measures are not assessed after a participant discontinues adalimumab. The exception to this will be the analysis of proportion of patients at 24 weeks who remain on adalimumab. Item level data on the PROs will be imputed according to the developers’ recommendations. Therefore, the analysis will be based on available data. The number of patients with missing data for each variable will be summarized and reported.

#### 4. SAMPLE SIZE AND POWER

Approximately 100 patients diagnosed with RA will be recruited per country. The sample size was calculated by assuming an alpha of 0.05 and a power of 0.80 in a two-sided test, resulting in 52 subjects required to recognize a statistically significant improvement in HAQ DI (-0.21) (11). Given the importance of other secondary endpoints, an improvement of  $9.9 \pm 25$  hours of work time lost requires 58 subjects, assuming an alpha of 0.05 and a power of 0.80 in a two-sided test (12). However, since it is expected that approximately half the study population may no longer be working due to their age, approximately twice this number (100 patients) will be required to achieve the required number of respondents. We have also assumed a drop-out rate of 13% (assuming between 10%-15%).

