9.5 Study Size

Approximately 89 patients diagnosed with RA will be recruited. The sample size was calculated by assuming an alpha of 0.05 and a power of 0.80 in a one-sided test, $Z(1-\alpha) = 1.645$ and $Z(1-\beta) = 0.842$. As to the primary variable, assuming a mean Δ HAQ-DI of -0.21 and a standard deviation (SD) of 0.5, according to the formula, 36 subjects are required. Then, given the importance of the secondary endpoint (WPAI), an improvement of 9.9 ± 25 hours of work time lost (mean=9.9, SD=25) requires 40 subjects. However, we assume a 50% employment rate in the study population and a drop-out rate of 10%, eventually approximately 89 patients will be required ($40/0.5/(1-0.1) = 89$).

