## 3. STUDY DESIGN

### 3.1 Overview of Study Design

This study is designed as a prospective, observational study to assess the effect of adalimumab on health-related QoL and work productivity in patients with RA in China, South Korea, and Taiwan in clinical practice.

RA patients will be recruited from within the clinical settings of each rheumatologist participating in the study. Approximately 243 patients diagnosed with RA that meet the inclusion and exclusion criteria will be enrolled at approximately 26 sites in China, South Korea and Taiwan.

To assess health and disability outcomes, the HAQ DI will be assessed at baseline, Week 12 and Week 24 after treatment initiation with adalimumab. In addition, other PROs of work activity and well-being, including the WPAI, EQ-5D-3L, and SF-36, will also be assessed.

The patients identified by the recruiting investigators (specialty dependent on country/region; e.g. rheumatologist, internists, general practitioners, etc.) based on the study selection criteria will complete a set of patient questionnaires on QoL, functioning, work productivity, treatment satisfaction, impression of change and HCRU. Data will be captured at baseline (D0), Week 12 and Week 24.

The HCRU will also be collected. This includes surgical procedures, hospitalizations, bed days in hospital, physician consultations etc. Costs will be assigned based on the HCRU using standardized costs for each participating countries.

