### 3.2 Study Population

Approximately 100 patients diagnosed with RA will be recruited per country from totally 26 sites. All eligible patients within the enrollment period will be included; inclusion and exclusion criteria for the population are as below.

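### SAP Section 4 loses its 13% drop-out when it doubles 58 to 100 instead of 116, so 100 per country gives about 72–74% power for work hours lost; its Korean size also disagrees with the protocol's 89

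*SAP*

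**What the plan says.** SAP Section 4 sets its error rates by "assuming an alpha of 0.05 and a power of 0.80 in a two-sided test". For the primary endpoint it reports "resulting in 52 subjects required to recognize a statistically significant improvement in HAQ DI (-0.21" points). For work productivity, an improvement of 9.9 ± 25 "hours of work time lost requires 58 subjects". Because about half the patients are expected not to be working, it concludes that "approximately twice this number (100 patients) will be required to achieve the required number of respondents". It then adds a 13% drop-out assumption (range 10–15%) without saying where that enters.

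Three other places give a size:

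- SAP 3.1: "Approximately 243 patients diagnosed with RA that meet the inclusion and exclusion criteria will be enrolled at approximately 26 sites", across China, South Korea and Taiwan.
- SAP 3.2: "Approximately 100 patients diagnosed with RA will be recruited per country from totally 26 sites".
- Protocol 9.5, for Korea alone: "eventually approximately 89 patients will be required". This uses a one-sided 5% test, 36 and 40 subjects, 50% employment and 10% drop-out.

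Protocol 9.7.3 makes every statistical test two-tailed at 0.05.

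**The concern.** The word approximately does not cover the step from 58 to 100. The text reads as if employment and drop-out had both been allowed for, yet the final number is smaller than the employment adjustment alone would give. If 100 carries no drop-out allowance, the 80% power claimed for work time lost is not delivered.

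That endpoint drives the size of the study, and the protocol's rationale wants the work-productivity data for reimbursement discussions. A non-significant result would be read against a power the plan does not have. The Korean report would also carry two incompatible size justifications, 100 two-sided and 89 one-sided.

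**Working it through.** **Inputs.** Two-sided alpha 0.05, power 0.80, change 9.9 with SD 25 hours, employment 50%, drop-out 13%, 100 per country (SAP Section 4). HAQ DI change −0.21 (SAP Section 4). The SAP gives no SD for HAQ DI; 0.5 is taken from Protocol 9.5 ("a standard deviation (SD) of 0.5, according to the formula, 36 subjects are required").

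**Reproducing 58 and 52.** For a paired change, n = (SD × (z₀.₉₇₅ + z₀.₈₀) / change)², with 1.960 + 0.842 for the z values.

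- Work time lost: n = 50.05 completers; 50.05/0.87 = 57.5, rounded up to 58.
- HAQ DI: n = 44.49 completers; 44.49/0.87 = 51.1, rounded up to 52.

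Both stated figures come out exactly, with the 13% already inside them. Without drop-out they would be 51 and 45. As a cross-check, 58 completers would give 85.4% power (normal), above the 80% target, so 58 is not the number of completers required.

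**The doubling step.** 58/0.5 = 116. The SAP's 100 matches 50.05/0.5 = 100.1, which is the doubled requirement before drop-out.

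**Power at 100 per country.** Employed completers: 100 × 0.5 × 0.87 = 43.5. Against the 50.05 needed this is 43.5/50.05 = 87%. Normal power = Φ((9.9/25) × √43.5 − 1.960) = Φ(0.652) = 74.3%. The paired-t figures use the noncentral t distribution.

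| Patients | Drop-out | Employed completers | Normal | Paired t |
|---|---|---|---|---|
| 100 | 0% | 50.0 | 80.0% | 78.4% |
| 100 | 10% | 45.0 | 75.7% | 73.8% |
| 100 | 13% | 43.5 | 74.3% | 72.3% |
| 100 | 15% | 42.5 | 73.3% | 71.3% |
| 116 | 13% | 50.5 | 80.3% | 78.8% |

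**HAQ DI at 100 per country.** 100 × 0.87 = 87 completers: 97.5% (normal) or 97.2% (paired t).

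**Korea at 89.** The protocol's chain reproduces: one-sided n = 39.4, rounded up to 40, and 35.05, rounded up to 36; 40/0.5/0.9 = 88.9, rounded up to 89. Employed completers are 89 × 0.5 × 0.9 = 40.05. Power for hours lost is 80.5% one-sided (normal). In the two-tailed test that Protocol 9.7.3 requires it is about 71% (normal) or 69% (paired t).

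**Totals.** 3 × 100 = 300 against 243. With Korea at 89, 243 − 89 = 154 would remain for the other two countries, against 200 at 100 each.

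**The case against.** Much can be said for the SAP. Its 52 and 58 are right by the normal formula, and its drop-out was applied at that step. The primary endpoint has ample power. SAP V0.2 is dated 2 January 2018. The amendment is dated 26 December 2017 in Protocol Section 5, but its approval dates run from 3 March to 12 April 2018, so Section 4 may simply carry the pre-amendment basis. The SAP also covers three countries, and the other protocols are not available here, so the source of 243 cannot be judged. All of this stands. It limits the point to one step, one secondary endpoint and a reconciliation, but it does not turn 100 into twice 58.

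A reader might infer more than the documents support:

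- **That 133 patients are needed (116/0.87).** This takes drop-out twice, since 58 already holds it.
- **That 43.5 completers meet only 75% of the need (43.5/58).** The 58 is a number before drop-out. Completers compare with about 50, which gives 87%.
- **That 52 and 58 are wrong because a paired t-test needs 47 and 53, inflated by 10% drop-out.** Those would be 52.2 and 58.9, rounding up to 53 and 59, and 10% is not the rate the SAP adopts. The normal formula with 13% fits exactly. Preferring t over z is a choice of method, not a correction of arithmetic.
- **That 72% is the power of the WPAI tests in SAP 5.4.** Those tests use percent overall work impairment and percent activity impairment. The planning figures are in hours, so the power does not carry over.

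**Conclusion.** The point holds. SAP Section 4 puts drop-out into 58 and loses it when doubling. By its own rule the size is about 116 per country, and 100 is 14% below that. At 100, power for work hours lost is about 74% (normal) or 72% (paired t), and it stays below 80% throughout the SAP's 10–15% drop-out range. The result assumes 50% employment, a change of 9.9 hours with SD 25, and that employment and drop-out are unrelated. That 58 includes the 13% is inferred from exact reproduction; the SAP does not say so.

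The primary HAQ DI analysis is not affected, given the protocol's SD of 0.5. Separately, the SAP's Korean size and basis disagree with the current protocol, the protocol's one-sided sizing disagrees with its own two-tailed tests, and the SAP's 243 disagrees with its 100 per country. These need reconciling, but the documents do not show which total is right for the three-country programme.

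**What to change.** 1. For Korea, replace 100 with 89 in SAP 3.2 and Section 4, and show the chain 89 × 0.5 × 0.9 = 40 employed completers.
2. State the two-sided power for hours lost at that size as about 71% (normal) or 69% (paired t). Name the method, and say that it applies to hours lost and not to the percent-impairment scores tested in SAP 5.4.
3. If 100 per country is kept for the other countries, correct the doubled figure to 116, say that 58 already includes 13% drop-out, and restate the power at 100 as about 74% (normal) or 72% (paired t).
4. Reconcile the 243 in SAP 3.1 with the per-country sizes. The figure of 89 can replace only the Korean number.

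The cost is SAP wording. No extra patients are needed; the stated power for the work-time endpoint falls.

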#### 5. STATISTICAL ANALYSIS

##### 5.1 General Considerations

The statistical analysis will be performed using SAS® 9.3 software or a later version (SAS Institute, North Carolina, USA) via SAS Enterprise Guide version 6.1. The statistical results will be displayed using tables, listings and/or graphs for each country. Figures will be performed with SAS®.

Unless otherwise specified, results will be provided as descriptive statistics by country. For categorical measures, data will include the frequency (number of cases [N]) and percentage (%) of total study patients observed in each category. Continuous variables will be described with number of patients with missing observations, mean, standard deviation (SD), median, minimum, and maximum.

The following rules will be followed to define the number of decimal positions to report in study results:

For categorical variables:

- 1 for the percentage.

For most of the continuous variables:

- 1 for the mean, SD, median, minimum, and maximum.
- In continuous variables with low values, 2 decimals for all measures will be reported.

A set of draft table shells (see the document, "AbbVie\_ROCKI\_Tableshell\_V0.2\_2Jan2018.xlsx") will be created in advance to

describe the statistical analysis that will be done to fulfill the objectives of this study. Based on the analysis results the tables will be modified accordingly.

## 5.2 Analysis Plan for Demographic and Clinical Characteristics

- Descriptive statistics will be presented for patient demographics (Excel Table 1), and clinical characteristics (Excel Table 2) for all patients by country. The following measures will be assessed as of the patient's baseline:
  - Patient age (mean, SD, minimum, maximum, median; categories: 18-34, 35-44, 45-54, 55-64, 65-74, 75+, missing)
  - Gender (male, female, missing)
  - Marital status (married, unmarried, missing)
  - Medical insurance type (National/Public insurance, Private insurance, Employer benefits, other, no insurance, missing)
  - Disease Activity Score in 28 joints - DAS28 (mean, SD, minimum, maximum, median; categories: Remission, Low Disease Activity, Moderate Disease Activity, High Disease Activity, Missing)
  - Number of patients with each of the comorbidities at baseline visit (See 3.5.2), and number of patients with any of these comorbidities

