4.0 Abstract

Title: Real-World Outcome of Rheumatoid Arthritis Patients in Korea on adalimumab (ROCKA Study).

Rationale and Background: Given the requirement to keep a balance between effectiveness and cost containment to ensure that the available health resources are used in a cost-effective manner, there is an increasing demand for real-world evidence (RWE) from policy makers, regulators, providers and payers in the region to optimize spending and patient outcomes.

So far, there are no data available regarding adalimumab's impact on patients' quality of life (QoL) and healthcare resource utilization (HCRU) in a realistic study design in Korea.

The goal of this study is to determine the QoL, HCRU and costs of the patients care in subjects with RA who are treated with adalimumab in Korea.

Results from study on the effect of adalimumab on Work Productivity and Activity Impairment (WPAI) scores and other Patient-Reported Outcomes (PROs) will be of interest to a variety of stakeholders in the healthcare system including patients, healthcare practitioners and payers in Korea.

Research Question and Objectives: The objective of this non-interventional, observational study is to assess the effect of adalimumab on health-related QoL and work productivity in patients with Rheumatoid Arthritis (RA) in Korea. Specifically, to achieve the above objective the following concrete steps will be taken:

1. Recruit investigators who are willing and able to recruit and follow new adalimumab users for 6 months follow-up
2. Collect the patients' clinical profile, patient-reported QoL, functioning, work productivity, treatment satisfaction and HCRU of RA patients at adalimumab initiation
3. Follow the patients initiating adalimumab for 24 weeks and identify the changes in clinical, economic, and PROs associated with adalimumab

Study Design: The study is designed as a prospective, observational study to assess the effect of adalimumab on health-related QoL and work productivity in patients with RA in Korea.

Note: This study is non-interventional and the subjects/investigators will follow the current clinical practice in each site and also the routine clinical follow up as determine by the treating physician.

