9.2 Setting

The study will take place in single country (Korea) with multiple centers. The study sites will be identified and selected by AbbVie. The study population shall comprise of male

and/or female patients who are attending a routine clinical visit and meet all of the inclusion criteria and none of the exclusion criteria. Overall, approximately 89 subjects with clinically diagnosed RA are planned to be enrolled in the study at up to 9 sites.

The recruiting investigators will select potentially eligible patients from consecutive visits within their clinic based on the inclusion and exclusion criteria (Section 9.2.1 and Section 9.2.2). It is the responsibility of each physician to ask every consecutive patient who meets the inclusion criteria of the study to participate to avoid selection bias, and if investigators hold different types of clinics (e.g. routine visit clinics versus emergency clinics), only patients visiting their routine clinics will be used for patient selection. Site personnel should thoroughly assess the eligibility criteria and evidence of this should be stored with the source documentation at site.

Where there is any deviation from the inclusion/exclusion criteria, the patient should be excluded from the study.

9.2.1 Inclusion Criteria:

Patients meeting all of the following inclusion criteria at baseline will be included:

1. Subject has a diagnosis of RA as defined by the 1987 revised ACR classification criteria and/or the ACR/ the European League against Rheumatism (EULAR) 2010 classification criteria (any duration since diagnosis)
2. Male or female subjects ≥ 18 years of age (local definition according to adalimumab label) who is in compliance with eligibility for adalimumab based on the local label
3. Patients with moderate to severe RA defined as DAS28 (ESR) or DAS28 (CRP) >3.2
4. Biologically treatment naïve and initiated adalimumab at baseline visit
5. Availability of clinical data of the previous 12 weeks prior to baseline
6. Ability to self-complete patient questionnaires
7. Subject must be able and willing to provide written informed consent and comply with the requirements of this study protocol

9.2.2 Exclusion Criteria:

Patients meeting any of the following exclusion criteria at baseline will be excluded:

1. Patients who are pregnant or breast feeding at enrolment or wish to become pregnant in the next 24 weeks

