9.2.4.7 Study Documents

Clinical case report form (CRF)

The clinical CRF will document the patient's current status (moderate, severe RA), Disease Activity Score in 28 joints (DAS28), prior and current treatments and other relevant clinical and demographic data to be used in segmenting the population during analysis.

To calculate the DAS28 the physician or specialist nurse will:

1. Count the number of swollen joints (out of the 28)
2. Count the number of tender joints (out of the 28)
3. Take blood to measure the erythrocyte sedimentation rate (ESR) or C reactive protein (CRP); the latest measurement in the medical records may also be used if a blood draw is not standard for that visit
4. Ask the patient to make a 'global assessment of health' which will be indicated by marking a 10 cm line between very good and very bad

The physician or specialist nurse will then mark each component score on the CRF and the DAS28 score if calculated (an online scoring calculator for the DAS28 can be found at <http://www.das-score.nl/das28/DAScalculators/dascalculators.html>).

The DAS28 will be scored using the following formula:

$$\text{DAS28 ESR} = 0.56 * \text{sqrt}(\text{tender28}) + 0.28 * \text{sqrt}(\text{swollen28}) + 0.70 * \ln(\text{ESR}) + 0.014 * (\text{Global assessment of Health in cm})$$

$$\text{DAS28 CRP} = 0.56 * \text{sqrt}(\text{tender28}) + 0.28 * \text{sqrt}(\text{swollen28}) + 0.36 * \ln(\text{CRP}) + 0.014 * (\text{Global assessment of Health in cm}) + 0.96$$

DAS28 scores will be interpreted using the following categorization:

- Remission: DAS28 \leq 2.6
- Low Disease activity: $2.6 < \text{DAS28} \leq 3.2$
- Moderate Disease Activity: $3.2 < \text{DAS28} \leq 5.1$
- High Disease Activity: DAS28 > 5.1

The full CRF is presented in Appendix C.

PRO questionnaires

The following PRO questionnaires will be included in the patient questionnaire packet.

Health Assessment Questionnaire Disability Index (HAQ DI)

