9.3 Variables

Variables:

Primary Variable

- Change in HAQ DI score at weeks 12 and weeks 24 weeks from the baseline

Secondary Variable

- Change in other PROs (SF-36 domain scales, EQ-5D Index, Work Productivity and Activity Impairment Questionnaire [WPAI]) from baseline to weeks 12 and 24
- Change in patient satisfaction questions from baseline to weeks 12 and 24
- Number and percent of patients achieving a clinically meaningful improvement on the HAQ DI, from baseline to weeks 12 and 24
- Healthcare Resource Utilization (HCRU) at baseline, 12 and 24 weeks

Additional Secondary Variable

- Change in HAQ DI score from baseline to 24 weeks
- Changes in the disease severity and PROs from baseline to 24 weeks

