### 3.2.1 ***Inclusion Criteria***

Patients meeting all of the following inclusion criteria at baseline will be included:

- Subject has a diagnosis of RA as defined by the 1987 revised ACR classification criteria and/or the ACR/ the European League against Rheumatism (EULAR) 2010 classification criteria (any duration since diagnosis)
- Male or female subjects  $\geq 18$  years of age (local definition according to adalimumab label) who is in compliance with eligibility for adalimumab based on the local label
- Patients with moderate to severe RA defined as DAS28 (ESR) or DAS28 (CRP) $>3.2$
- Biologically treatment naïve and initiated adalimumab at baseline visit
- Availability of clinical data of the previous 12 weeks prior to baseline
- Ability to self-complete patient questionnaires
- Subject must be able and willing to provide written informed consent and comply with the requirements of this study protocol

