#### **5.5 Analysis Plan for Additional Secondary Objectives**

- Descriptive statistics will be presented for post-index overall RA related direct healthcare resource utilization (Excel Table 8)

- Consultations/visits to healthcare professionals for treatment of RA (number of patients with  $\geq 1$  visit; categorized by the treatment department listed in 3.5.4)
- Procedures received when visiting the healthcare professional(s) for treatment of RA (number of patients with  $\geq 1$  procedure; categories listed in 3.5.4)
- surgeries received when visiting the healthcare professional(s) for treatment of RA (number of patients with  $\geq 1$  surgery; categories listed in 3.5.4)
- Hospitalizations in relation to RA (number of patients with  $\geq 1$  admission)
- Length of stay in days (mean, SD, median)
- Concomitant medications taken for RA (number of patients with  $\geq 1$  medication; categories listed in 3.5.4))

- Associations between disease severity (measured by DAS28) and PROs (HAQ DI score, SF-36 domain scales, EQ-5D-3L index, WPAI outcomes) will be analyzed using the bivariate linear regression model (Excel Table 9.1). Separate models will be estimated to identify the association between DAS28 and each of the PROs.
- Additionally, in Excel Table 9.2, separate bivariate liner regression models will be estimated to identify the association between change in DAS28 and change in each of the PROs at 12 and 24 weeks after baseline respectively.

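### The SAP describes DAS28 only at baseline and afterwards uses its change only as an association with PRO change, so a variable listed in the protocol gets no estimate of its own

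*SAP*

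**What the plan says.** **Protocol.** Section 9.3 includes among the additional secondary variables "Changes in the disease severity and PROs from baseline to 24 weeks". Step 3 of the objectives in the Abstract is to follow patients for 24 weeks and "identify the changes in clinical, economic, and PROs associated with adalimumab". The schedule in 9.1.1 has DAS28 at baseline, Week 12, Week 24 and early termination. Section 9.7.3 asks for descriptive analysis of all key parameters, and for change from initiation to 24 weeks to be calculated and evaluated for improvement. The specific analysis list in 9.7.6 is narrower. For severity it names only associations with PROs, and associations of change with change.

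**SAP.** Section 5.2 (Excel Table 2) describes DAS28 as of baseline by mean, SD, range, median and "categories: Remission, Low Disease Activity, Moderate Disease Activity, High Disease Activity, Missing". Section 5.5 then plans Table 9.1, relating DAS28 to each PRO with no visit stated, and Table 9.2, the "association between change in DAS28 and change in each of the PROs at 12 and 24 weeks after baseline respectively". The table list in section 6 gives Week 12 and Week 24 change tables for HAQ DI, SF-36, EQ-5D-3L, WPAI and satisfaction. It gives none for DAS28.

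**Entry rule.** Protocol 9.2.1 admits "Patients with moderate to severe RA defined as DAS28 (ESR) or DAS28 (CRP) >3.2", and SAP 3.2.1 repeats the criterion.

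**The concern.** The protocol names change in disease severity as a variable and collects DAS28 at every visit, but the SAP plans no summary of how DAS28 changes. The remission and low-activity rows appear at the one visit where eligibility is meant to keep them empty. They do not appear at the visits where they would be informative.

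At stake is whether the report can say how disease activity moved and how many patients reached low activity or remission. DAS28 is the efficacy measure that uses joint counts and a laboratory marker. The effect estimates that do have change tables are patient questionnaires completed by people who know they have started a biologic. SAP 5.1 also allows the table shells to be modified in the light of the results, so a DAS28 change table added later could look chosen after the fact.

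**Working it through.** The plan states no figure on this point to reproduce. The check has four parts.

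**1. Table count.** SAP section 6 lists 12 tables: 1, 2, 3.1, 3.2, 4, 5, 6, 7, 8, 9.1, 9.2 and 10. Reading each title with its section 5 description:
- DAS28 described on its own: Table 2, baseline only.
- DAS28 change at Weeks 12 and 24: Table 9.2, as an association.
- DAS28 against PROs with no visit stated: Table 9.1.
- Follow-up DAS28 level, mean change, interval or category count: 0 of 12.

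**2. What Table 9.2 can show.** Let x be DAS28 change and y be PRO change, with fitted line y = a + b·x. The slope is b = cov(x, y)/var(x). Adding a constant c to every x leaves b unchanged, so the same slope fits a cohort that improved, stayed level or worsened on average. Because mean(y) = a + b·mean(x), a reader could recover mean(x) only if the intercept were printed, b were not zero, and mean(y) were given for the same patients. The SAP commits to none of this. Even then there would be no SD, interval or category count.

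**3. Entry rule against the categories.** Protocol 9.2.4.7 and SAP 3.5.2 share the same cut-offs: remission is DAS28 ≤ 2.6, and low activity is above 2.6 and up to 3.2. Entry needs DAS28 > 3.2. If Table 2 uses the same version and formula as eligibility, the expected baseline count in both categories is 0.

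**4. Whether version and formula are the same.** Eligibility accepts the ESR or the CRP version, and the SAP does not say which is tabulated. The CRP formulas differ:
- Protocol 9.2.4.7: the CRP term is 0.36 × ln(CRP), plus a constant of 0.96.
- SAP 3.5.2: one formula with 0.70 × ln(ESR or CRP) and no constant.

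SAP minus protocol, CRP version = 0.34 × ln(CRP) − 0.96. This is zero at CRP = exp(0.96/0.34) = 16.8 mg/L and negative below that.

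| CRP (mg/L) | SAP − protocol | Protocol scores that the SAP formula puts at or below 3.2 |
|---|---|---|
| 1 | −0.96 | above 3.2, up to 4.16 |
| 2 | −0.72 | above 3.2, up to 3.92 |
| 5 | −0.41 | above 3.2, up to 3.61 |
| 10 | −0.18 | above 3.2, up to 3.38 |
| 30 | +0.20 | none |

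Illustration with assumed values: 8 tender joints, 6 swollen joints, CRP 2 mg/L, global assessment 6 cm.
- Protocol: 0.56√8 + 0.28√6 + 0.36 ln 2 + 0.014 × 6 + 0.96 = 1.58 + 0.69 + 0.25 + 0.08 + 0.96 = 3.56, eligible.
- SAP: 1.58 + 0.69 + 0.70 ln 2 + 0.08 = 1.58 + 0.69 + 0.49 + 0.08 = 2.84, low activity.

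The conflict also affects change scores. The constant cancels but the coefficient does not. Each halving of CRP moves the score by −0.36 × 0.693 = −0.25 under the protocol and −0.70 × 0.693 = −0.49 under the SAP.

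**The case against.** The strongest defence is that the SAP does what the protocol's specific analysis list asks. Protocol 9.7.6 turns severity change into an association with PRO change, and SAP 2.3 and Table 9.2 implement that. DAS28 is neither the primary nor a main secondary endpoint. The table shells sit in a separate workbook that could hold more than the list shows. SAP 3.5 says most variables are measured at all three visits, so Table 9.1 may also use follow-up values.

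Much of this stands. A reader might infer that post-baseline DAS28 goes unanalysed, or that DAS28 change is the protocol's clinical outcome. The documents support neither: its change is derived and analysed at both follow-up visits, and it is an additional secondary variable. A reader might also call DAS28 the only measure from clinician and laboratory. It contains a patient global rating, it is scored by clinicians who know the treatment, and the clinician CRF also records surgeries, length of stay and medications. Nor must the two lower categories be empty at baseline; part 4 of the working shows how eligible patients could fall into them. Listing all four categories there does no harm and could expose entry or formula errors.

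What the defence does not meet is 9.3 together with 9.7.3. The first lists the change as a variable in its own right, and the second asks for change to 24 weeks to be calculated and evaluated. An association does neither in a form a reader can use.

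**Conclusion.** The gap is real and modest. On the SAP text and table list, DAS28 change is analysed only as an association and is never summarised as an outcome, so an additional secondary variable of the protocol has no mean change, interval or responder count. The primary analysis and the sample size are unaffected.

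The protocol's planning figures imply about 80 patients followed to Week 24 (89 × 0.9 = 80.1). That is not a count of usable scores: the CRF asks for the latest DAS28 only where one has been calculated, and an older laboratory value may be used.

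The conclusion assumes that the unseen shells add no DAS28 change table. The statement that the lower categories should be empty at baseline further assumes one DAS28 version and formula throughout, which the documents do not currently provide.

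**What to change.** 1. Reconcile the CRP-based formula between protocol 9.2.4.7 and SAP 3.5.2. State one formula for each version, including the unit of the global assessment, which the protocol gives as centimetres and the SAP formula leaves unstated. Require the same version within each patient at all visits. This comes first, because otherwise CRP-based changes and categories would depend on which document the programmer followed.
2. Add one table to the SAP, next to Table 3.1. It should give DAS28 at baseline, Week 12 and Week 24; mean change with SD and 95% CI by the same paired method as HAQ DI; n and % in each of the four categories at each visit; and the number of patients with a DAS28 score at each visit. A baseline-to-Week-24 category shift table is optional.
3. State the visit or visits used in Table 9.1.

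The cost is one descriptive table from data already scheduled, plus the formula reconciliation. The SAP change should be dated before the follow-up DAS28 results are seen.
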